Reassessment of serological response was originally planned at one year to evaluate the rate of persistent response. This time point was previously chosen in the general population, and subjects were found to have persistent immunity.³ It was also assessed in a recent phase III trial evaluating response to another inactivated herpes zoster vaccine in immunocompromised patients undergoing autologous stem cell transplant. They were also found to have persistent response.¹³ Due to the COVID-19 pandemic and closure of research laboratories the one year sample could not be collected. The sample will instead be collected at 24 months \pm 3 months. A recent study demonstrated persistent response to the Shingrix vaccine in healthy adults up to 10

years after the initial dose³⁴, suggesting that the 24-month collection is a reasonable time point for reassessment.

This study is designed to obtain valid and comparable results to measure response to a vaccine in a vulnerable population in a fast and uncomplicated way.

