3.2. Inclusion and Exclusion Criteria

a) Inclusion Criteria:

Patients will be eligible if:

- They are at least 50 years of age;
- Have been diagnosed with chronic lymphocytic leukemia (CLL) OR Waldenström macroglobulinemia (WM);
- Have been on first-line BTK inhibitor (i.e. ibrutinib or acalabrutinib) for at least 3 months;
- Prior treatment with single agent rituximab is permitted if the last dose was administered more than one year ago;
- Have at least a one-year life expectancy;
- Have a history of varicella (chicken-pox) OR lived in the US or any endemic country for > 30 years'
- Prior radiation therapy is allowed

b) Exclusion Criteria:

Patients will be excluded from the study if they:

- Have a known hypersensitivity to a vaccine component;
- Have had herpes zoster reactivation within the past year;
- Received or were scheduled to receive a live virus vaccine in the period from 4 weeks prior to Dose 1 through 28 days post-second dose;
- Received or were scheduled to receive an inactivated vaccine in the period ranging from 7 days prior to Dose 1 through 7 days post-second dose;
- Are unable to give informed consent;
- Have an absolute lymphocyte count greater than $20,000 \times 10^9/L$;
- Are receiving treatment for CLL or WM with an additional agent other than a BTK inhibitor;

- Had rituximab treatment less than one year prior to study start;
- Had prior chemotherapy.

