5.2. Efficacy Assessments

Vaccine response, as determined by blood antibody levels to the varicella virus glycoprotein E subunit (anti-gE), will be measured by ELISA. This humoral response will be assessed four weeks after vaccination is complete. In patients who were seropositive before the study, a positive response will be defined as at least a four-fold increase in geometric mean concentration (GMC) of anti-VZV gE antibody as measured per ELISA. Humoral response in seronegative patients at baseline will be defined as at least a four-fold increase from the lower detection limit of the anti-gE antibody assay.

Secondary efficacy objectives include:

1. Measure humoral response at 24 months post-vaccination, which is defined as persistence of anti-gE antibody above test threshold at 24 months.
2. Measure cell-mediated response to vaccination at one month and 24 months after vaccination.
3. Evaluation of CLL/WM progression on BTK inhibitor as determined by treating oncologist at latest assessment, and correlation between progression on BTK inhibitor and vaccine response at 4 weeks and at 24 months post-second dose.

Cellular-mediated response will be determined by measuring PBMC activation (by ELISPOT or flow cytometry) following stimulation with varicella glycoprotein E peptide. PBMC activation at 4 weeks and 24 months post dose will be compared to pre-vaccination activation levels.

a. Safety Assessments

Subjects will be educated to recognize immediate adverse reactions to the vaccine. Patient-reported signs of allergic or hypersensitivity reactions will be assessed and managed by the study team as needed. Only severe adverse effects will be captured in this study. Subjects will be contacted 4 weeks \pm 1 week after each dose of the vaccine for assessment and their chart will be reviewed at the same moment. Severe adverse effects are defined as any grades 3-5 adverse effects included in the CTCAE v5.0 classification.

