13. DATA ANALYSIS AND MONITORING

13.1. Sample Size Determination

The primary endpoint for assessing the immunological response to the vaccine has been defined in section 5.2. The target accrual will be 30 evaluable subjects receiving treatment with BTK inhibitor. Allowing for 10% drop-out due to subject participation or lab testing issues, this trial will accrue a total of 33 CLL or WM patients. Based on current estimates, the expected time to accrue these subjects is 6 months.

We expect that the response to vaccine will be significantly less than the 97% response rate seen in the healthy general population. The table below shows the exact Clopper-Pearson two-sided 90% confidence intervals for a range of likely observed response rates for a range of sample sizes. The upper bound of the 90% (two-sided) confidence interval corresponds to a (one-sided) 95% confidence interval. Therefore, with 30 evaluable subjects and observed response rate

<85%, we will have 95% confidence that the true immunological response rate is less than the general population response rate.

Table 3: Two-sided 90% Confidence Intervals for a range of potential response rates by sample size

Immunologic Response Rate (%)	Sample Size		
	20	25	30
25	10 – 46%	12 – 43%	13 – 41%
35	18 – 56%	19 – 53%	21 – 52%
45	26 – 65%	28 – 63%	29 – 61%
55	35 – 74%	37 – 72%	39 – 71%
65	44 – 82%	47 – 81%	48 – 79%
75	54 – 90%	57 – 88%	59 – 87%
85	66 – 96%	68 – 95%	70 – 94%

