13.2. Planned Statistical Analysis

13.2.a Primary Analysis

The estimates of geometric mean antibody titers pre- and post-vaccination, mean fold-changes, and vaccine response rates will be described with 90% (two-sided) confidence intervals. These estimates will be important for designing a future vaccine trial in patients treated with BTK inhibitors with emergence of shingles as the primary outcome. Self-reported and chart-reviewed serious adverse events will be summarized in tabular format by type and grade.

13.2.b Secondary and Exploratory Analyses

As secondary analyses, the change in antibody titers pre and post-vaccination will be evaluated with the Wilcoxon Rank Signed Test for paired data. This test will provide some indication whether the within subject change in titer is statistically different from zero. The change in seroprotection rates pre and post vaccination will be assessed by the exact McNemar test for paired proportions.

As exploratory analyses, the association between baseline characteristics and the achievement of immunological response and change in antibody titers will be assessed using exact non-parametric statistical tests, such as exact Chi-Square test, Wilcoxon Rank Sum test, or Spearman rank correlation tests, depending on the scale of the variables involved. Baseline characteristics of particular interest have been described above and include age, stage at diagnosis, time since diagnosis, presence of high-risk or low-risk features, time since BTK inhibitor therapy initiation, history of zoster reactivation, IgG levels at study entry and use of rituximab therapy. These results will be reported along with descriptive statistics for the purpose of hypothesis generation in future trials.

The disease progression to BTK inhibitor at visit 4 and visit 5 will be determined from the closest assessment by treating oncologist. The association between vaccine response and disease progression at each time point will be assessed with Fisher's exact test.

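### The 24-month humoral response has no baseline reference, so antibody present before vaccination can count as vaccine response

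*Combined protocol and SAP*

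**What the plan says.** Section 5.2 uses two different rules for humoral response.

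- **4 weeks, baseline seropositive:** "In patients who were seropositive before the study, a positive response will be defined as at least a four-fold increase".
- **4 weeks, baseline seronegative:** "Humoral response in seronegative patients at baseline will be defined as at least a four-fold increase from the lower detection limit".
- **24 months, everyone:** "Measure humoral response at 24 months post-vaccination, which is defined as persistence of anti-gE antibody above test threshold at 24 months".

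The first two measure change. The third is an absolute status at one visit.

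Section 3.2 makes prior exposure an entry condition: "Have a history of varicella (chicken-pox) OR lived in the US or any endemic country for > 30 years". Section 2.2 explains why there is neither a placebo group nor a healthy control group.

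Section 13.2.b then uses response at both visits: "The association between vaccine response and disease progression at each time point will be assessed" with Fisher's exact test. Section 5.2 confirms that the response meant is the one at 4 weeks and the one at 24 months. Section 13.2.b also plans a pre/post comparison of a yes/no status: "The change in seroprotection rates pre and post vaccination will be assessed by the exact McNemar test for paired proportions". The word *seroprotection* occurs only there and has no cut-off.

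**The concern.** In a single-arm trial, only the patient's own baseline separates antibody raised by the vaccine from antibody that was already there. The 4-week rule uses that baseline and the 24-month rule does not. The plan itself expects some patients to be seropositive before dose 1, since it gives them their own 4-week rule. Such a patient can fail the four-fold test at 4 weeks and still be a humoral responder at 24 months with no change in titre.

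Two results are exposed. The first is the 24-month response rate, a named secondary objective. It can exceed the 4-week rate for reasons unrelated to the vaccine. The second is the visit 5 Fisher test, which would relate progression to something other than what the visit 4 test does, although both carry the label of vaccine response.

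**Working it through.** **Inputs from the document**
- 30 evaluable patients (Sections 3.1 and 13.1).
- Two-sided 90% confidence intervals (Section 13.2.a), exact Clopper-Pearson in Section 13.1.
- The response rules of Section 5.2, as above.
- The visit 5 blood draw is optional (Table 1), and patients who miss it are not replaced (Section 3.1).

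**Assumptions, not in the document**
- s of the 30 patients are seropositive at baseline, with s = 20, 25 or 29.
- The 24-month test threshold is the same cut-off that defines serostatus. Section 5.2 uses the terms *lower detection limit* and *test threshold* without saying that they coincide.
- All 30 give the visit 5 sample.
- Antibody is stable and the vaccine has no effect.

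**Step 1: reproduce the plan's intervals.** For x responders of n, the lower limit is the 0.05 quantile of Beta(x, n − x + 1) and the upper limit is the 0.95 quantile of Beta(x + 1, n − x). For the 85% row at n = 30, x = 0.85 × 30 = 25.5, which gives 70.1% to 94.3%. Table 3 prints 70–94%. All 21 cells of Table 3 reproduce in this way. The plan gives no figure for the 24-month endpoint or the McNemar test.

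**Step 2: classify each patient when the vaccine does nothing.**
- Seropositive at baseline: the fold-change at 4 weeks is 1, below 4, so not a responder. At 24 months the antibody is above threshold, so a responder.
- Seronegative at baseline: below the limit at both visits, so not a responder at either.

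The 4-week rate is therefore 0/30, with upper limit 1 − 0.05^(1/30) = 9.5%. The 24-month rate is s/30.

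| Seropositive at baseline (assumed) | 4-week response (90% CI) | 24-month response (90% CI) |
|---|---|---|
| 20/30 | 0% (0–9.5%) | 67% (50–81%) |
| 25/30 | 0% (0–9.5%) | 83% (68–93%) |
| 29/30 | 0% (0–9.5%) | 97% (85–99.8%) |

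**Step 3: relax stability.** If 20% of baseline seropositives fall below threshold by 24 months, the rate is 0.8 × s/30: 53%, 67% and 77%.

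**Step 4: room to show an effect.** With stable old antibody, a fully effective and fully persistent vaccine gives 30/30. It then differs from no effect by only 30 − s patients: 10, 5 or 1.

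**Step 5: the Fisher tests.** In the Step 2 cohort, the visit 4 test has no responders to compare. The visit 5 test compares patients who were seropositive with those who were seronegative before vaccination, so it tests baseline serostatus and not vaccine response.

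**Step 6: the McNemar wording.** Suppose seroprotection means serostatus. A patient positive at both visits is then concordant, whatever the fold-rise. With b gains and no reversals, the two-sided p is 2 × 0.5^b: 0.125 for b = 4, 0.0625 for 5, 0.031 for 6 and 0.002 for 10. Reversals count against the vaccine: 6 gains and 1 reversal give p = 0.125. Suppose instead that it means the four-fold response. The pre-vaccination rate is then zero by construction, and 6 responders of 30 already give p = 0.031. Under a protective titre set above the detection limit, some seropositive patients could still convert. The result depends on a definition that the plan does not give.

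**The case against.** The strongest reply is that a null vaccine effect could not stay hidden. The 4-week response rate, the geometric mean titres and fold-changes, the signed-rank test and the three-visit mixed model would all show it. The late draw is also described as a check on persistence, which may have been meant to apply only to patients who responded at 4 weeks. Both 24-month and 4-week definitions are openly stated. Finally, prior exposure is not the same as detectable antibody: Section 1.2 describes hypogammaglobulinemia in CLL, so baseline seropositivity might be low.

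Much of this stands. The titre analyses do protect the overall reading of the trial, and the size of the problem depends on an unknown share. But no condition on 4-week response is written. The mixed model describes titres and does not correct a reported response rate or the visit 5 Fisher test. The direction of the error is the same for any non-zero share of seropositive patients whose antibody stays above threshold.

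A reader might infer three stronger things, none of which the document supports.

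- **That the McNemar test ignores every baseline-seropositive patient and contradicts the primary endpoint.** This needs a definition of seroprotection that the plan does not supply and a significance level that it does not state. Positive-to-negative changes also count.
- **That the 24-month rate will look like that of healthy people.** Section 13.1 expects a response "significantly less than the 97% response rate seen in the healthy general population", but that figure is the benchmark for the 4-week response. The match with 29/30 is a coincidence of the assumed share.
- **That the trial would report success for an ineffective vaccine.** The primary estimates would show otherwise.

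**Conclusion.** The concern holds for the 24-month secondary endpoint and its Fisher test. As written, the rule counts pre-vaccination antibody as vaccine response. With no vaccine effect it would give 67% to 97% across the assumed range of 20 to 29 of 30 seropositive at baseline, against 0/30 at 4 weeks. These figures also rest on the threshold being the serostatus cut-off, full attendance at an optional visit and stable antibody. A higher threshold or waning would lower them, and incomplete attendance would change the denominator and widen the intervals.

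The primary 4-week estimates, the signed-rank test and the mixed model are unaffected. The change should be made, but it concerns secondary analyses only. The McNemar wording is a minor clarification of an undefined term.

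**What to change.** **24-month endpoint and its Fisher test (Sections 5.2 and 13.2.b).** Choose one of two rules and use it in both places:
- apply the four-fold rule of Section 5.2 at 24 months, against the patient's own baseline, or against the detection limit for baseline seronegatives; or
- define persistence only among patients who responded at visit 4.

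Report the proportion above test threshold separately, split by baseline serostatus, with the number actually sampled at visit 5 as denominator. State whether the test threshold and the lower detection limit are the same value.

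**McNemar test (Section 13.2.b).** Define seroprotection and its cut-off, show the paired 2×2 table from baseline to visit 4, and label the p-value descriptive.

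**Timing.** When this version was written, "the one year sample could not be collected" (Section 2.2), so the study was already well under way. If titres have been seen, report the current and the new definition side by side and mark the new one as post hoc.

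**Cost.** Wording only, with the same samples and assays. The reported 24-month rate will probably be lower under the four-fold rule, or rest on fewer patients if restricted to visit 4 responders. Groups split by baseline serostatus may be very small.

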2.2. Rationale for Study Design

Evidence exists that patients over 50 years old in the general population and immunocompromised patients with hematologic conditions can achieve serologic response to Shingrix.³ However, response seems to be less in patients with CLL or indolent lymphoma¹³ and patients treated with BTK inhibitors have yet to be studied. Our study specifically targets that population through a simple trial that will address whether these patients can truly benefit from the vaccine.

The vaccine is indicated in our planned patient population, but we do not understand its efficacy and we do not know optimal timing for vaccination while on BTK inhibition. There is evidence of vaccine response in a subset of immunocompromised patients with minimal toxicity.^{13,14} A placebo group was not included because it was perceived as possibly unethical to take away their possibility to receive the vaccine.

The decision was also made not to include a healthy control group since the primary objective of the study is to assess the response rate in our population, not to compare it with the general population. Moreover, a study with over 3000 healthy patients shows robust response data in almost 100% of subjects, which we can use to indirectly compare our response rates.³ Prior studies in vulnerable populations have used the same design with valid results. Toxicity rates did not result any higher than in the general population in these studies. It is not expected to be higher in our population.

Assessment of serological response at four weeks was planned in our study in accordance with previous vaccination literature. This time point is known to represent the end of primary immunity response, which is a marker of immunologic response. Assessing a clinical endpoint (reactivation of herpes zoster) would have necessitated a larger cohort of patients followed for several years, which is not the objective of a pilot study. This could ultimately be done in further studies if response is noted in this trial.

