3.3. Discussion of Subject Population

Inclusion and exclusion were selected to include a homogeneous CLL and WM population treated with BTK inhibitors. Special consideration was taken to avoid disease heterogeneity in order to obtain valid results and this is why only patients who have been on a first-line BTK inhibitor for at least 3 months will be included.

The age limit was set at 50 years old as per the vaccine label.

Exclusion criteria were the result of contra-indications to the vaccine or to the inability to correctly undergo all steps in the research process. In our population, a considerable number of patients also received concomitant rituximab for a period of 6 months (weekly for 1 month and monthly until month 6) at treatment initiation in the context of a clinical trial. We decided not to exclude these patients, but to restrict their enrollment to those who have not had rituximab in the last 12 months. The 12-month time limit was set to minimize the prolonged side effects of rituximab on immunity, but to maximize the inclusion of patients. Data published by Anolik et al in 2006 showed that, although incomplete, B cell recovery occurred by 12 months.²⁹ Even though retrospective data shows that 38.9% of patients with non-Hodgkin's lymphoma develop new-onset hypogammaglobulinemia at a median of 1.4 years post-treatment with a median of 7 doses of rituximab³⁰ and multiple case reports of prolonged hypogammaglobulinemia, happened in the context of rheumatologic diseases or concomitant chemotherapy,³¹⁻³³ this data does not represent our population and thus cannot be applied to them. Currently, no such data exists for this population.

Exclusion of subjects with absolute lymphocyte counts greater than 20,000 cells/ μ L was decided empirically to avoid interference with the assays. An excessive number of lymphocytes could potentially interfere with the laboratory analyses.

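### Eligibility links concomitant rituximab to longer time on BTK inhibitor, but section 13.2.b tests the two characteristics only one at a time

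*Combined protocol and SAP*

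**What the plan says.** Protocol section 3.3 explains that many local patients "also received concomitant rituximab for a period of 6 months (weekly for 1 month and monthly until month 6) at treatment initiation", as part of a clinical trial. They are not excluded; the plan is to "restrict their enrollment to those who have not had rituximab in the last 12 months". Section 3.2 gives the matching exclusion, "Had rituximab treatment less than one year prior to study start". It also opens a second route to past rituximab: "Prior treatment with single agent rituximab is permitted if the last dose was administered more than one year ago". For everyone, the BTK inhibitor requirement is "Have been on first-line BTK inhibitor (i.e. ibrutinib or acalabrutinib) for at least 3 months".

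Section 5 records past rituximab as yes or no, with the number of cycles and the date of the last one, and records the date BTK inhibitor therapy began.

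Section 13.2.b lists, among the baseline characteristics of particular interest, "time since BTK inhibitor therapy initiation, history of zoster reactivation, IgG levels at study entry and use of rituximab therapy". Their association with response and with titre change is to be assessed by exact chi-square, rank-sum or Spearman tests, according to scale. The stated purpose is to generate hypotheses for later trials. The same section plans a linear mixed model for the markers over time that controls for baseline characteristics it does not name.

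**The concern.** Whether rituximab exposure or time on BTK inhibitor goes with a poorer or better response is one of the few questions beyond the primary estimate on which this pilot can offer a lead. Section 2.2 raises the timing question itself: "we do not know optimal timing for vaccination while on BTK inhibition". Section 3.3 shows a parallel worry about lasting effects of rituximab on immunity.

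The eligibility rules leave a stretch of short BTK exposure in which no completed concomitant course can occur. A one-variable test of rituximab then compares groups that also differ in time on drug, and a one-variable test of time compares groups that also differ in rituximab history. A real effect of one can appear as an effect of the other, or hide it. This can be known before any data are seen, and the plan does not mention it. At stake is which hypothesis is carried into a later trial.

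**Working it through.** The plan states no figure on this point, so there is none to reproduce. The 18 months below is derived, and the sizes come from simulation on stated assumptions.

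**Step 1: minimum time on BTK inhibitor.**
- Completed concomitant course (3.3): 6 months of rituximab from treatment start + 12 months without it = 18 months.
- Course stopped after the first month: 1 + 12 = 13 months.
- No rituximab, or single-agent rituximab before the BTK inhibitor (3.2): 3 months.

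**Step 2: what eligibility alone does to mean duration.** Assume durations spread evenly from the minimum to an upper limit U, the same in both groups. The means are (18 + U)/2 and (3 + U)/2, a gap of 15/2 = 7.5 months whatever U is. If rituximab-free patients are instead assumed to stop at 24 months while rituximab patients run to 48, the means are 33 and 13.5, a gap of 19.5 months. The extra (48 − 24)/2 = 12 months comes from the assumed upper limits, which no eligibility rule sets.

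**Step 3: effect on the test of response.** Inputs: 30 evaluable patients (13.1). Assumed: 10 rituximab users and 20 others; when only time matters, odds of response multiplied by 2.7 per 12 months on drug; when only rituximab matters, response 20% with it and 60% without.

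| Assumed durations (months), rituximab / none | Spurious rituximab difference | Fisher rejections | Time test rejections when only rituximab matters |
|---|---|---|---|
| 18–48 / 3–24 | about 34 points | about 31% | 33–35% |
| 18–48 / 3–36 | about 24 points | about 14% | 18–19% |
| Same upper limit, 48 or 60 | 12–14 points | 5–8% | 7–8% |
| Same upper limit, 3 of the 10 users earlier single-agent | 8–9 points | about 4–5% | not needed here |

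For scale, with response near 50% the standard error of a difference between 10 and 20 patients is √(0.25/10 + 0.25/20) = 0.19, or 19 points. A bias of 8 to 14 points is below one standard error.

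**Step 4: effect on the tests of a continuous titre change.** Assumed: concomitant share 20–40%, earlier single-agent share 0–15%, the same upper limit in both groups, and 2,000 trials per setting at a nominal two-sided 5%. Time correlates about 0.5 with outcome when only time matters; rituximab shifts the outcome by 1 SD when only rituximab matters.

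| Upper limit (months) | Correlation of the two variables | False positives, rituximab | False positives, time |
|---|---|---|---|
| 36 | 0.22–0.41 | 9–17% | 8–15% |
| 48 | 0.16–0.30 | 5–12% | 6–12% |
| 72 | 0.10–0.20 | 5–7% | 5–7% |

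With both variables in one linear model, both false-positive rates are 4–6% in every setting.

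**Step 5: would restriction be enough?** In the 18–48 / 3–24 setting, comparing rituximab groups only at 18 months or more leaves about 6 rituximab-free patients. About 19 points of spurious difference remain, because 18–48 is still being compared with 18–24. Testing time only in rituximab-free patients cuts power for a real time effect from about 59% to 17%.

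**The case against.** The case for leaving the plan alone has real force. These tests are labelled exploratory, and no decision or sample size rests on them. Correlated characteristics are a general limit of one-variable tests in 30 patients, and age, stage and time since diagnosis share it. The large simulated figures need unequal upper limits on BTK duration that no eligibility rule creates. The recorded yes/no variable pools concomitant users with earlier single-agent users, who may have only 3 months on BTK inhibitor, and this weakens the link. The mixed model might also adjust for both variables.

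Most of this stands, and it limits size and severity. Two parts do not dispose of the point. The mixed model commits to no covariates, describes markers over time, and does not cover response as a yes/no outcome. And this link, unlike the general one, is built in by the protocol's own rules, so it can be handled in advance.

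A reader might infer that every rituximab user has at least 18 months on the drug, or that eligibility by itself produces a difference of some 34 points. The documents support neither. The 18-month minimum applies to completed concomitant courses only, and nothing in the protocol stops rituximab-free patients from having long exposure.

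**Conclusion.** The concern holds as a minor point. Eligibility ties a completed concomitant rituximab course to about 18 months or more on BTK inhibitor, against 3 months for others, and the planned one-variable tests cannot separate the two characteristics.

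For response, the likely size runs from small (about 8 to 14 points of spurious difference, 4 to 8% rejections, with a shared upper limit of 48 or 60 months) to about 34 points and 31% if all rituximab-free patients have short exposure. For titre change, false-positive rates range from about 5% to 17%, the higher values arising when the shared upper limit is as low as 36 months. All of these rest on an assumed share of concomitant users, spread of durations and effect strength, none of which the documents give.

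A reader might take this as a threat to the trial's main result. It is not: the primary response rate and its interval use neither variable.

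**What to change.** In section 13.2.b:

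1. Keep the planned one-variable tests, and state that the results for rituximab use and for time since BTK inhibitor initiation are confounded by eligibility.
2. Classify rituximab history as concomitant, earlier single-agent or none, and cross-tabulate it with BTK duration, so that the actual overlap is visible.
3. Add an analysis holding both variables: a two-variable regression for log titre change, and an exact or penalised logistic model for response. The 4–6% error rates above were shown for the linear model.
4. Report time since BTK initiation in rituximab-free patients, and the rituximab comparison among patients with at least 18 months on BTK inhibitor, as supportive sensitivity analyses only. Restriction loses too many patients, and can leave too much bias, to be the main answer.

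The dates needed are already collected under section 5. The cost is a few sentences, a little more analysis work, and wide intervals with 30 patients.
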